## 2. SUMMARY OF KEY PROTOCOL INFORMATION

### 2.1. Changes to the Protocol Defined Statistical Analysis Plan

There were changes to the originally planned statistical analysis specified in the protocol amendment 05 (Dated: 30JUN2016) of study CTT116855 [GlaxoSmithKline Document Number [2013N176913\\_05](#)].

The protocol only states that comparisons of FF/UMEC/VI with FF/VI and with UMEC/VI will be performed. In addition, comparisons of UMEC/VI with FF/VI will also be performed for all endpoints.

Additional endpoints to those mentioned in the protocol will be analyzed as listed below. These are related to protocol-defined endpoints and will be used to further characterize the effects of FF/UMEC/VI, FF/VI and UMEC/VI.

#### **COPD Exacerbations:**

- Time to first on-treatment moderate/severe exacerbation by Eosinophil subgroup (comparing FF/UMEC/VI with FF/VI)
- Time to each on-treatment moderate/severe exacerbation  
Time to first on-treatment severe exacerbation by Eosinophil subgroup
- Time to first on-treatment mild/moderate/severe exacerbation
- Time to first on-treatment moderate exacerbation
- Time to first on-treatment exacerbation requiring systemic/oral corticosteroids
- Time to first on-treatment exacerbation requiring antibiotics

#### **Spirometry:**

- Change from baseline in trough FEV1 by Eosinophil subgroup
- FEV1 reversibility
- Percentage of subjects with an increase from baseline in trough FEV1  $\geq 100$ mL
- Percentage of subjects with an increase from baseline in trough FEV1  $\geq 100$ mL by Eosinophil subgroup
- Change from baseline in trough Forced Vital Capacity (FVC)
- Change from baseline in post-bronchodilator FVC

**All Cause Mortality:**

- Time to death from any cause (on and off treatment)

**SGRQ:**

- Change from baseline in SGRQ Total score by Eosinophil subgroup
- Proportions of responders according to the SGRQ Total score by Eosinophil subgroup

**TDI:**

- TDI focal score comparing FF/UMEC/VI with UMEC/VI (note, the comparison of FF/UMEC/VI with FF/VI is in the protocol)
- TDI Focal Score by Eosinophil subgroup
- Proportion of responders according to TDI
- Proportion of responders according to TDI by Eosinophil subgroup

**CAT:**

- Change from baseline in COPD Assessment Test (CAT) score by Eosinophil subgroup
- Proportion of responders according to CAT score by Eosinophil subgroup

**Daily Diary:**

- Change from baseline in mean nighttime awakenings per night due to COPD symptoms
- Change from baseline in the percentage of days symptoms stopped usual activities

**Composite Endpoints:**

- Time to first event in the pneumonia AESI group and moderate/severe COPD exacerbation composite
- Time to first event in the pneumonia AESI group resulting in hospitalization, prolonged hospitalization or death and severe COPD exacerbation composite
- Time to first event in the pneumonia AESI group resulting in hospitalization, prolonged hospitalization or death, event in the CV AESI group resulting in hospitalization, prolonged hospitalization or death and severe COPD exacerbation composite

Even though some endpoints only state one treatment comparison, all treatment comparisons (FF/UMEC/VI compared with FF/VI, FF/UMEC/VI compared with UMEC/VI and UMEC/VI compared with FF/VI) will be performed and displayed for completeness for all endpoints except for J2R sensitivity analyses.

The Safety Analyses section of the protocol includes reference to analyses of time to first pneumonia and time to first hospitalization for pneumonia. The analyses are clarified in this RAP as time to first event in the ‘Pneumonia’ Adverse Event of Special Interest (AESI) group and time to first event in the ‘Pneumonia’ AESI group resulting in hospitalization, prolonged hospitalization or death.

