6.3.2.2. Definition of an SAE

A serious adverse event is any untoward medical occurrence that, at any dose:

- a. Results in death
- b. Is life-threatening

NOTE: The term 'life-threatening' in the definition of 'serious' refers to an event in which the subject was at risk of death at the time of the event. It does not refer to an event, which hypothetically might have caused death, if it were more severe.

- c. Requires hospitalisation or prolongation of existing hospitalisation

NOTE: In general, hospitalisation signifies that the subject has been detained (usually involving at least an overnight stay) at the hospital or emergency ward for observation and/or treatment that would not have been appropriate in the physician’s office or out-patient setting. Complications that occur during hospitalisation are AEs. If a complication prolongs hospitalisation or fulfills any other serious criteria, the event is serious. When in doubt as to whether “hospitalisation” occurred or was necessary, the AE should be considered serious.

Hospitalisation for elective treatment of a pre-existing condition that did not worsen from baseline is not considered an AE.

- d. Results in disability/incapacity, or

NOTE: The term disability means a substantial disruption of a person's ability to conduct normal life functions. This definition is not intended to include experiences of relatively minor medical significance such as uncomplicated headache, nausea, vomiting, diarrhea, influenza, and accidental trauma (e.g. sprained ankle) which may interfere or prevent everyday life functions but do not constitute a substantial disruption.

- e. Is a congenital anomaly/birth defect
- f. Medical or scientific judgment should be exercised in deciding whether reporting is appropriate in other situations, such as important medical events that may not be immediately life-threatening or result in death or hospitalisation but may jeopardise the subject or may require medical or surgical intervention to prevent one of the other outcomes listed in the above definition. These should also be considered serious. Examples of such events are invasive or malignant cancers, intensive treatment in an emergency room or at home for allergic bronchospasm, blood dyscrasias or convulsions that do not result in hospitalisation, or development of drug dependency or drug abuse.

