8.3.5.2. Safety Analyses

The extent of exposure to study drug will be summarized by treatment group, using the statistics n, mean, SD, median, minimum and maximum.

AEs and SAEs occurring pre-treatment, during active treatment and post-treatment will be summarized separately. The number and percentage of subjects experiencing at least one AE of any type, AEs within each body system and AEs within each preferred term will be presented for each treatment group. Separate summaries will be provided for all AEs, drug-related AEs, SAEs, and for AEs leading to permanent discontinuation of study drug or withdrawal from the study.

Time to first event in the Pneumonia Adverse Event of Special Interest subgroup and time to first serious event in the Pneumonia Adverse Event of Special Interest subgroup will be analysed using Cox's proportional hazards model. Deaths due to pneumonia will be summarised and tabulated.

Incidence of bone fractures will be summarised. Full details will be given in the RAP.

Incidence of cardiovascular events (including supraventricular arrhythmia and non-fatal myocardial infarction) will be summarised.

All laboratory parameters will be summarised and tabulated.

A pre-specified MACE analysis (broad analysis and narrow analysis) will be performed using adjudicated cardiovascular deaths and other non-fatal SAEs. MACE events to be included in both the broad and narrow analysis would be defined *a priori*.

Full details of the analyses to be performed on all safety endpoints will be given in the RAP.

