~~In addition to the sensitivity analysis using any post-treatment data collected from subjects during the study, the pattern of missing data due to study withdrawals will be examined to determine if the missing data at random assumption for the analysis of exacerbation rate is met. To further examine any effect of study withdrawals, a supporting analysis of the rate of exacerbations will be performed on <1-year intervals (e.g. quarterly intervals), and study withdrawals will also be presented in graphical display (e.g., Kaplan-Meier plot of study withdrawals).~~

The secondary endpoints of trough (pre-dose AM) FEV₁ and SGRQ total score will be analysed using mixed models repeated measures with covariates of treatment group, smoking status at screening, baseline, region, and visit, plus interaction terms for visit by baseline and visit by treatment group.

The secondary endpoints involving time to first moderate and/or severe exacerbation will compare the treatment groups using Cox's proportional hazards model, adjusting for treatment group, gender, exacerbation history (one, two or more), smoking status at screening, baseline disease severity (as % predicted FEV₁), screening blood eosinophil level and geographical region.

Secondary and other endpoints involving the annual rate of exacerbations will be analysed as described for the primary endpoint.

The additional endpoint of time to onset of multiple moderate and severe exacerbations will be analysed using an Anderson-Gill model for time to recurrent events.

Full details of the analyses to be performed on all primary, secondary and other efficacy endpoints will be given in the RAP.

In Section 8.3.5.2 Safety Analyses the text was modified to clarify analysis of pneumonia events and MACE analysis.

The extent of exposure to study drug will be summarized by treatment group, using the statistics n, mean, SD, median, minimum and maximum.

AEs and SAEs occurring pre-treatment, during active treatment and post-treatment will be summarized separately. The number and percentage of subjects experiencing at least one AE of any type, AEs within each body system and AEs within each preferred term will be presented for each treatment group. Separate summaries will be provided for all AEs, drug-related AEs, SAEs, and for AEs leading to permanent discontinuation of study drug or withdrawal from the study.

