**9.2.13.2. Time to First Event in the Pneumonia AESI Group, Cardiovascular AESI Group**

Safety Statistical Analyses Time to First Pneumonia
Endpoint

 
• Time to first on-treatment event in the Pneumonia AESI group
 
• Time to first on-treatment event in the Pneumonia AESI group resulting in hospitalization, prolonged hospitalization or death.
 
• Time to first on-treatment event in the Cardiovascular AESI group
 
• Time to first on-treatment event in the Cardiovascular AESI group resulting in hospitalization, prolonged hospitalization or death.
 

Model Specification

 
• Cox's proportional hazards model
 
• Terms in the model:               
 
• Response: time to first event in the Pneumonia/Cardiovascular AESI group (definition dependent on endpoint)
 
• Categorical: treatment group, geographical region
 
 
 
• The 'exact' method will be used for handling ties. If the analysis will not run using the 'exact' method, then the 'Efron' method for handling ties will be used instead.
 
• Kaplan-Meier survivor functions will be obtained for each treatment group using PROC LIFETEST with a TIME statement.
 

Model Checking & Diagnostics

 
• Refer to Appendix 10: Model Checking and Diagnostics for Statistical Analysis.
 

Model Results Presentation

 
• Hazard ratios (and percent reduction in risk for pairwise treatment comparisons with associated 95% CIs and unadjusted p-values will be presented.
 
• The probability of having an event, 95% CI and first quartile and median time to event for each treatment group will be presented.
 
• The Kaplan-Meier curves will be presented showing the probability of having an event over time for each treatment group separately plotted on the same figure. This will be repeated displaying FF/VI and UMEC/VI treatment groups only.
 

Example SAS Code
<pre>proc phreg data=dsetin;   class trtcd region;   model timeto1*eventflag(0) = trtcd region / risklimits ties=exact;   hazardratio trtcd / diff=all; run;  proc lifetest data=destin outsurv=survest;   time timeto1*eventflag(0);   strata trtcd; run;</pre>

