Hospitalization/prolongs existing hospitalization	
Results in disability/incapacity	
Congenital anomaly/birth defect	
Other (medically significant)	
Possible drug-induced liver injury	
Adverse events leading to permanent discontinuation of study treatment or withdrawal from study	
Psychiatric disorders	Psychiatric disorders (SOC)
Nervous system disorders	Nervous system disorders (SOC)
Accidents and injuries	Accidents and injuries (SMQ)
Cardiac disorders	Cardiac disorders (SOC)
Vascular disorders	Vascular disorders (SOC)
Cerebrovascular disorders	Central nervous system vascular disorders (SMQ)
Infections and infestations	Infections and infestations (SOC)
Anticholinergic syndrome	Anticholinergic syndrome (SMQ)
Quality of life decreased	Quality of life decreased (PT)
Postural hypotension, Falls, Black outs/Syncope, Dizziness, Ataxia and Fractures	Postural hypotension (selected PTs*), Falls (PT), Black outs/Syncope (selected PTs*), Dizziness (selected PTs*), Ataxia (selected PTs*) and Fractures (selected PTs*)

* Preferred terms which contribute to each of the groups will be provided by GCSP using the MedDRA version current at the time of reporting. This will be finalised prior to unblinding.
	
Association to Serious Adverse Reports	

An event in the pneumonia AESI group is considered associated with an adjudicated Serious Adverse Report if the Serious Adverse Report was classified as 'COPD exacerbation with evidence of pneumonia' or 'Pneumonia/respiratory tract infection without COPD exacerbation' and the onset of the Serious Adverse Report is within -7 to +10 days of the onset of the pneumonia AESI.
	

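### SAP 2.1 misdescribes the protocol's serious-pneumonia analysis, and the SAP models a narrower hospital-or-death endpoint instead of time to first serious pneumonia event

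*SAP*

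**What the plan says.** **Protocol 8.3.5.2 (Safety Analyses)** commits to two Cox analyses for pneumonia. One is time to first event in the AESI subgroup. For the other, "time to first serious event in the Pneumonia Adverse Event of Special Interest subgroup will be analysed" by the same method.

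**SAP 2.1** sets amendment 05 as its reference point: "There were changes to the originally planned statistical analysis specified in the protocol amendment 05". At the end of that section it describes the protocol's pneumonia analyses: "The Safety Analyses section of the protocol includes reference to analyses of time to first pneumonia and time to first hospitalization for pneumonia". It then presents its own definitions as a clarification of that text.

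**SAP 9.2.13.2** gives the second endpoint as "Time to first on-treatment event in the Pneumonia AESI group resulting in hospitalization, prolonged hospitalization or death". Table 3.044 and Figures 3.06-3.07 carry the same definition.

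**Protocol 6.3.2.2** defines a serious event by seven criteria, (a) to (g). Death and hospitalisation (including a prolonged stay) are two of them. Another is "Is life-threatening", and disability and important medical events are also listed.

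**The concern.** The SAP describes a protocol analysis that is not in the amendment it names, and then builds its second pneumonia endpoint on that description. As a result, an analysis the protocol commits to is not produced, and SAP 2.1 does not show the reader that it was replaced or why.

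This matters because pneumonia is the first risk listed in protocol 1.3.1 and is named as a key ICS risk in 1.3.3. There is also a practical problem. Tables 3.042 and 3.044 both sit under the SAP's heading for serious AESIs, but the first counts all serious events and the second only the hospital-or-death subset. Their counts can differ without any explanation in the plan.

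**Working it through.** The documents give no event count or power for the pneumonia analyses, so there is no planned figure to reproduce. The check is a comparison of texts, followed by an illustration of size.

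**1. Is the conflict between current texts?** Yes. It is between protocol 8.3.5.2 and SAP 2.1 and 9.2.13.2. The protocol's amendment log (11.5.5) shows only where the SAP's wording came from. It records "In Section 8.3.5.2 Safety Analyses the text was modified to clarify analysis of pneumonia events and MACE analysis", and the marked-up text there strikes out the hospitalisation wording and inserts serious event. SAP 2.1 therefore clarifies wording that amendment 05 had removed.

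**2. Which seriousness criteria does the SAP endpoint keep?**

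| Protocol 6.3.2.2 criterion | Counted in SAP endpoint |
|---|---|
| (a) death | yes |
| (b) life-threatening | no |
| (c) hospitalisation or prolonged stay | yes |
| (d) disability/incapacity | no |
| (e) congenital anomaly | no |
| (f) important medical event | no |
| (g) possible drug-induced liver injury | no |

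Every event in the SAP endpoint is serious, but not every serious pneumonia is in the endpoint. Criteria (b), (d) and (f) could realistically apply to a pneumonia; (e) and (g) hardly could.

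**3. Does the protocol's analysis appear elsewhere in the SAP?** No.
- The pneumonia models in 9.2.13.2 and the model-checking list in 11.10.1.2 cover any event, or the hospital-or-death subset.
- The eosinophil version in 9.2.13.3 is any event.
- The composites in 9.2.13.4 and 9.2.13.5 use any event, or the hospital-or-death subset.

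**4. Where do the omitted events still count?**
- The any-pneumonia Cox model (Table 3.036) and its eosinophil repeat (Table 3.037).
- The composite with moderate/severe exacerbation (Table 3.052).
- Table 3.041, whose pneumonia AESI summary is repeated for serious events (SAP 9.2.3.1).
- Table 3.042, with rates per thousand subject-years (SAP 11.5.4.2).

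**5. Size, as an illustration only.** Inputs from the documents are 4,000 FF/UMEC/VI and 2,000 UMEC/VI subjects (protocol 8.2.1), and pneumonia in 6-7% on FF/VI against 3% on VI (protocol 1.3.1). The assumptions are that those rates carry over to these two arms, that 30-70% of pneumonias are serious, and that 2-20% of serious ones qualify only on other criteria, in the same proportion in each arm.

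- Lowest number of serious first events: (4,000 × 6% + 2,000 × 3%) × 30% = 300 × 30% = 90.
- Highest: (4,000 × 7% + 2,000 × 3%) × 70% = 340 × 70% = 238.
- Events omitted: from 90 × 2% ≈ 2 to 238 × 20% ≈ 48.

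Schoenfeld power for d events with 2:1 allocation at two-sided 5% is Φ(√(d × 2/3 × 1/3) × |ln HR| − 1.96). In the smallest case HR = ln(1 − 0.018)/ln(1 − 0.009) ≈ 2.01.

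- All 90 events: √20 × 0.698 − 1.96 = 1.16, power 88%.
- 10% lost (81 events): power 84%.
- 20% lost (72 events): √16 × 0.698 − 1.96 = 0.83, power 80%.

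In the other cases examined, losing 20% costs about 3 percentage points or less.

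**The case against.** The strongest defence is that little is lost and nothing is hidden. SAP 2.1 states its definition in full, in a section headed as changes to the protocol, and the endpoint, table and figure titles repeat it. SAP 2.2 keeps serious pneumonia as a named incidence endpoint. Protocol 6.3.2.2 defines hospitalisation broadly enough to include detention in an emergency ward, so few serious pneumonias should fall outside the subset. The hospital-or-death definition also matches the one used for cardiovascular AESIs and for the pneumonia eCRF tables.

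Most of this stands, and it rules out several stronger readings that a reader might infer:
- *That serious pneumonias disappear from safety reporting.* They do not; the displays in step 4 retain them.
- *That a pre-specified comparison of FF-containing arms with UMEC/VI is lost.* Protocol 8.3.5.2 names no contrast for the pneumonia models. The SAP supplies all three pairwise contrasts.
- *That the hazard ratio is biased in favour of the ICS arms.* Nothing in the documents shows bias in either direction.
- *That the analysis carries special rank.* The protocol calls pneumonia a key risk; it does not rank this model above the any-pneumonia one.

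The defence does not answer the central point. Stating the new definition is not the same as declaring that it replaces a protocol analysis, and here it is set against wording the protocol no longer contains. A descriptive table of serious events is not a time-to-first-event comparison.

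**Conclusion.** The point holds as a mismatch between protocol and SAP on one safety model. SAP 2.1 misdescribes amendment 05. Following the SAP leaves time to first serious Pneumonia AESI event unanalysed and puts a strict subset in its place. The effect is confined to that Cox and Kaplan-Meier analysis and to the two composites that use the same definition (Tables 3.053 and 3.054). Those composites are SAP additions, so their definition does not itself breach the protocol.

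The text comparison rests on no assumption. The size does: the documents give no figure, and the 2 to 48 events depend on assumed fractions and on incidence rates borrowed from earlier FF/VI studies. Because a serious pneumonia will usually involve admission, the lower part of that range is more plausible; that is a judgement. The reason to act is that a pre-specified safety analysis should be produced and described correctly.

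**What to change.** 1. In SAP 9.2.13.2, add time to first on-treatment serious event in the Pneumonia AESI group, counting any seriousness criterion, with the same Cox model as the existing endpoints. Add it to the model-checking list in 11.10.1.2.
2. Add one Cox table and two Kaplan-Meier figures (all three arms; FF/VI and UMEC/VI only) to the display lists.
3. Keep the hospital-or-death endpoint, Table 3.044 and Figures 3.06-3.07 as an additional analysis. The composites can stay as defined.
4. Rewrite the closing paragraph of SAP 2.1 so that it gives the amendment 05 wording and declares the narrower endpoint as an addition to the protocol.

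Correcting 2.1 and declaring the narrower endpoint as a reasoned replacement would cure the misdescription, but the protocol's analysis would still not be produced.

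The cost is one model, one table, two figures and a paragraph. No new data are needed: the reasons for seriousness are already due to be listed (Listing 22). The SAP synopsis says final-analysis decisions are made by Source Data Lock, so the change should be made before then.

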**2.2. Study Objectives and Endpoints**

Objectives
Primary Objective

 
To evaluate the efficacy of FF/UMEC/VI to reduce the annual rate of moderate/severe exacerbations compared with dual therapy of FF/VI or UMEC/VI in subjects with COPD
 

Secondary Objectives

 
To evaluate the long term safety and other efficacy assessments of FF/UMEC/VI compared with dual therapy of FF/VI or UMEC/VI
 
To evaluate the efficacy of FF/UMEC/VI to reduce exacerbations compared with UMEC/VI in the subset population of subjects with a screening eosinophil count <math>\geq 0.15 \times 10^9/L</math>
 

Other Objectives

 
To evaluate the patient perspective of the efficacy of FF/UMEC/VI in subjects with COPD
 
To evaluate the population pharmacokinetic (PK) profiles of FF, UMEC and VI in subjects with COPD
 
To collect blood samples for a genetics research study
 

Note: PK and genetics analyses as well as any analysis performed on the single biomarker (fibrinogen) data collected for this study will be detailed in separate RAPs.

Endpoints
Co-Primary Treatment Comparisons on the Primary Efficacy Endpoint

 
Annual rate of on-treatment moderate/severe exacerbations comparing FF/UMEC/VI with UMEC/VI
 
Annual rate of on-treatment moderate/severe exacerbations comparing FF/UMEC/VI with FF/VI
 

Secondary Efficacy Endpoints and Treatment Comparisons

 
Change from baseline in trough FEV1 at Week 52 comparing FF/UMEC/VI with FF/VI
 
Change from baseline in SGRQ Total Score at Week 52 comparing FF/UMEC/VI with FF/VI
 
Time to first on-treatment moderate/severe exacerbation comparing FF/UMEC/VI with FF/VI and with UMEC/VI
 
Annual rate of on-treatment moderate/severe exacerbations comparing FF/UMEC/VI with UMEC/VI in the subset of subjects with a blood eosinophil count <math>\geq 0.15 \times 10^9/L</math>
 
Time to first on-treatment moderate/severe exacerbation comparing FF/UMEC/VI with
 

Endpoints

UMEC/VI in the subset of subjects with a blood eosinophil count <math>\geq 0.15 \times 10^9/L</math>
 
 
• Annual rate of on-treatment severe exacerbations comparing FF/UMEC/VI with FF/VI and with UMEC/VI
 

Other Efficacy Endpoints

 
• Annual rate of all on-treatment exacerbations (mild, moderate, severe)
 
• Annual rate of on-treatment moderate exacerbations
 
• Annual rate of on-treatment exacerbations requiring systemic/oral corticosteroids
 
• Annual rate of on-treatment exacerbations requiring antibiotics
 
• Annual rate of on-treatment severe exacerbations by Eosinophil subgroup (note, annual rate of on-treatment moderate/severe exacerbations comparing FF/UMEC/VI with UMEC/VI in the subset of subjects with a blood eosinophil count <math>\geq 0.15 \times 10^9/L</math> is a secondary endpoint)
 
• Time to first on-treatment mild/moderate/severe exacerbation
 
• Time to first on-treatment moderate exacerbation
 
• Time to first on-treatment COPD exacerbation requiring systemic/oral corticosteroids
 
• Time to first on-treatment exacerbations requiring antibiotics
 
• Time to first on-treatment severe exacerbation
 
• Time to first on-treatment moderate/severe exacerbation by Eosinophil subgroup (note: time to first on-treatment moderate/severe exacerbation comparing FF/UMEC/VI with UMEC/VI in the subset of subjects with a blood eosinophil count <math>\geq 0.15 \times 10^9/L</math> is a secondary endpoint)
 
• Time to first on-treatment severe exacerbation by Eosinophil subgroup
 
• Time to each on-treatment moderate/severe exacerbation
 
• Time to each on-treatment severe exacerbation
 
• Time to death from any cause (on-treatment only)
 
• Time to death from any cause (on and off treatment)
 
• Change from baseline in trough FEV1 (note, comparing FF/UMEC/VI with FF/VI at Week 52 is a secondary endpoint)
 
• Change from baseline in trough FEV1 by Eosinophil Subgroup
 
• Percentage of subjects with an increase from baseline in trough FEV1 <math>\geq 100mL</math>
 
• Percentage of subjects with an increase from baseline in trough FEV1 <math>\geq 100mL</math> by Eosinophil Subgroup
 
• Change from baseline in post-bronchodilator FEV1
 
• FEV1 reversibility
 
• Change from baseline in trough FVC
 
• Change from baseline in post-bronchodilator FVC
 
• Change from baseline in SGRQ Total score (note, comparing FF/UMEC/VI with FF/VI at Week 52 is a secondary endpoint)
 

Endpoints

 
• Change from baseline in SGRQ Total score by Eosinophil Subgroup
 
• Proportion of responders according to the SGRQ Total score
 
• Proportion of responders according to the SGRQ Total score by Eosinophil Subgroup
 
• Change from baseline in CAT score
 
• Change from baseline in CAT score by Eosinophil Subgroup
 
• Proportion of responders according to the CAT score
 
• Proportion of responders according to the CAT score by Eosinophil Subgroup
 
• TDI focal score (in a subset of subjects)
 
• TDI focal score by Eosinophil Subgroup
 
• Proportion of responders according to TDI
 
• Proportion of responders according to TDI by Eosinophil Subgroup
 
• Subject global rating of activity limitation and subject global impression of change in activity limitation
 
• Subject global rating of severity of COPD and change in COPD severity
 
• Change from baseline in use of rescue albuterol/salbutamol (occasions/day)
 
• Change from baseline in percentage of rescue-free days
 
• Change from baseline in mean number of nighttime awakenings per night due to COPD symptoms
 
• Change from baseline in the percentage of days symptoms stopped usual activities
 

Safety Endpoints

 
• Incidence of adverse events (AEs). To include: 
 
○ AEs collected on the eCRF page
 
○ SAEs collected on the eCRF page
 
○ AEs of Special Interest
 
○ SAE's of Special Interest
 
○ Fatal On-treatment AE's of Special Interest
 
 
 
• Adjudicated Serious Adverse Reports
 
• Incidence of pneumonia. To include: 
 
○ Pneumonia details collected on the eCRF page
 
○ Events in the Pneumonia AEs of Special Interest Group
 
○ Serious events in the Pneumonia AE's of Special Interest Group
 
 
 
• Incidence of cardiovascular events. To include: 
 
○ MACE
 
○ Events in the Cardiovascular AEs of Special Interest Group
 
 
 

Endpoints


• Events in the pneumonia AESI group and moderate/severe exacerbations composite

• Events in the pneumonia AESI group leading to hospitalization, prolonged hospitalization or death and severe exacerbations

• Events in the pneumonia AESI group resulting in hospitalization, prolonged hospitalization or death, severe exacerbation and event in the cardiovascular AESI group resulting in hospitalization, prolonged hospitalization or death

• ECG measurements

• Vital signs

• Hematological and clinical chemistry parameters

• Oropharyngeal examinations (reported as part of the AEs)

• Incidence of bone fractures

Health Outcome Endpoints

• EuroQol Questionnaire (EQ-5D-5L)

• Healthcare resource utilization (all-cause and COPD related)

